#### **9.2.8.2 Exploratory Blood Collection**

Blood for genomic DNA will be collected as per the Study Flow Chart (Appendix 1 and 2) at Visit 2/Baseline and Visit 6/Day 14 and Visit 8/Day 28/Early Termination and stored for potential gene array analysis or additional exploratory testing at a later date.

Blood for essential lipid analysis will be collected as per Study Flow Chart (Appendix 1 and 2) at Visit 2/Baseline, Visit 6/Day 14 and Visit 8/Day 28/Early Termination and analysed at a later date.

### **9.2.8.3 Biomarker Blood Collection**

Blood for biomarkers will be collected as per the Study Flow Chart (Appendix 1 and 2) at Visit 2/Baseline, Visit 3/Day 3, Visit 4/Day 5, Visit 5/Day 7, Visit 6/Day 14, Visit 7/Day 21, Visit 8/Day 28/Early Termination and will be stored for later biomarker analysis.

### **9.2.9 Adverse Event Assessment**

See Section 11.

### **9.2.10 Concomitant Medication**

All administered concomitant medications should be recorded throughout the study.

Patients should avoid both during the study and for 4 weeks prior to baseline, ingesting food supplements rich in omega-3 or omega-6 fatty acids (e.g., cod liver oil capsules).

### **9.2.11 Liver Ultrasound**

A liver ultrasound will be conducted at screening which, in conjunction with patient history and clinical examination, will eliminate other causes of liver disease including biliary obstruction, hepatocellular carcinoma and Budd Chiari syndrome.

### **9.2.12 Bioanalysis**

Human plasma levels of 15(S)-HEPE will be determined using validated liquid chromatography tandem mass spectrometry (LC-MS/MS) methods and conducted at Charles River Laboratories Edinburgh Ltd.

### **9.2.13 Sample Storage, Handling and Shipping**

Sample storage, handling and shipping will be done as per standard operating procedures and as specified in the laboratory procedures manual.

### **9.2.14 Liver Histopathology**

For patients who have liver biopsies as part of their clinical care before and/or during the study, liver histopathology results will be reported in the eCRF

### **9.2.15 Urinalysis**

pH, protein, glucose, blood, ketones, leukocytes, leukocyte esterase, bilirubin, specific gravity, urobilinogen and nitrate will be assessed. Reflex micro to be done locally if blood, protein, leukocyte esterase or nitrate/nitrite are present.

Note: Urinalysis assessment will be conducted at screening only.

## 10 INVESTIGATIONAL PRODUCT/INVESTIGATIONAL DRUG

The following medication supplies will be used in the study:

### **DS102 Capsule:**

Description:

White, opaque hard-shelled capsule (size 0) containing 500mg of 15-HEPE EE with 5% w/w of colloidal silicon dioxide as viscosity modifier.

### **DS102 Placebo (Paraffin Oil):**

Description:

White, opaque hard-shelled capsule (size 0) containing equivalent fill weight of liquid paraffin with 1% w/w of colloidal silicon dioxide as viscosity modifier.

### **10.1 Supply, Packaging, Labelling, Handling and Storage**

The study treatment is capsules of 15-HEPE EE or placebo. DS102 (15(S)-HEPE EE) will be provided by Afimmune.

DS102 and Placebo capsules will be stored at 2 – 8°C in a secure area (e.g., a locked refrigerator or drug storage room), protected from unintended use.

The test materials will be identified by the batch numbers and expiry date.

Labelling, packaging and release will be in accordance with the Clinical Trials Directive 2001/20/EC and GMP Directive 2003/94/EC as for Investigational Medicinal Products and Annex 13 of the GMP Guide. Labels will be blinded to the dose and contain the randomisation number. In addition, DS102 (15(S)-HEPE EE) and placebo capsules will be labelled with information according to local regulations.

### **10.2 Dosage and Administration**

Patients who fulfil all inclusion and no exclusion criteria may be accepted in the study. Each patient must read and sign an ICF prior to any screening procedures being performed. This study involves a comparison of DS102 with placebo, administered orally within 30 minutes after a meal twice daily for a total duration of 28 days. Patients will also receive standard of care therapy in addition to their assigned IMP throughout the treatment period of the study. The last study drug administration should occur on the day preceding Visit 6/Day 28/Early Termination.

[figure not shown]
Patients will be randomised to one of the two treatment groups in a 1:1 ratio:

- Treatment group A: 2 x placebo 500mg capsules orally administered BD (four capsules daily) for 28 days

- Treatment group B: 2 x DS102 500mg capsules orally administered BD (four capsules daily) for 28 days

Patients will be required to take the capsules within 30 minutes after a meal. Medication(s) for other conditions that are permitted in the study can be taken as usual.

Walleted blister packs will consist of seven days of four capsules. Patients will be instructed to take the two capsules **from left to right**, on the relevant day, as shown below:

### 10.3 Duration of Treatment

Patients will take assigned medication for 28 consecutive days.

### 10.4 Drug Accountability

The Investigator is responsible for maintaining accurate records of the study medication received initially, the study drug dispensed/used, the returned medication by patients (in the case of patients discharged prior to 28 days) and the medication returned to the Sponsor or designee for destruction. All study drug accountability forms and treatment logs must be retained in the ISF. These records must be available for inspection by the Sponsor, its designees or by regulatory agencies at any time.

Used drug boxes/blister packs will be stored safely until destruction and must be accounted for by the Investigator. The study monitor will perform drug accountability for all study drug at the site and assist in returning study drug, including used and unused study drug, to the Sponsor or designee. After verification of the drug accountability by the Sponsor, the Investigator will ensure proper destruction or return of the remaining study product.

---

Any study medication accidentally or deliberately destroyed will need to be accounted for. Any discrepancies between amounts dispensed and returned will need to be explained.

## 11 ADVERSE EVENTS AND SERIOUS ADVERSE EVENTS

### 11.1 Definitions of Adverse Events

#### 11.1.1 Seriousness

##### **Adverse Events (AE):**

An AE is defined as any undesirable experience occurring to a patient that has signed the ICF and who has taken their first dose of the study drug, whether or not considered related to the IMP(s). All AEs must be recorded in the eCRF, defining relationship to IMP and severity. AEs should also be recorded by the Investigator in the patient file/notes.

##### **Serious Adverse Events (SAE):**

If a patient experiences a SAE after the first dose of the study drug, the event will be recorded as a SAE.

*A SAE (experience) or reaction is any untoward medical occurrence that at any dose:*

- results in death
- is life-threatening
- requires in-patient hospitalisation or prolongation of existing hospitalisation
- results in persistent or significant disability/incapacity, or
- is a congenital anomaly/birth defect

Note: the term “life-threatening” in the definition of “serious” refers to an event in which the patient was at risk of death at the time of the event. It does not refer to an event which hypothetically might have caused death if it were more severe.

Medical and scientific judgment should be exercised in deciding whether expedited reporting is appropriate in other situations, such as important medical events that may not be immediately life-threatening or result in death or hospitalisation but may jeopardise the patient or may require intervention to prevent one of the other outcomes listed in the definition above. These should also usually be considered serious.

Examples of such events are intensive treatment in an emergency room or at home for allergic bronchospasm, blood dyscrasias or convulsions that do not result in hospitalisation, or development of drug dependency or drug abuse.

##### **Unexpected Adverse Event (UAE):**

A UAE is defined as an experience not previously reported in the Investigator's Brochure (IB) or similar product information sheet such as the Summary of Products Characteristics (SPC).

### 11.1.2 Severity

The intensity of an AE is an estimate of the relative severity of the event made by the Investigator based on his or her clinical experience. The following definitions are to be used to rate the severity of an AE:

- Mild: the AE is transient and easily tolerated.
- Moderate: the AE causes the patient discomfort and interrupts the patient's usual activities.
- Severe: the AE causes considerable interference with the patient's usual activities, and may be incapacitating or life-threatening.

### 11.1.3 Relationship to IMP

The Investigator will establish causality of the AE to experimental treatment. The Investigator should take into account the patient's history, most recent physical examination findings, and concomitant medications.

The following definitions will be used to determine causality of an AE:

- Not related: temporal relationship of the onset of the AE, relative to the experimental treatment is not reasonable or another cause can explain the occurrence of the AE.
- Related: temporal relationship of the onset of the AE, relative to the experimental treatment is reasonable, follows a known response pattern to the treatment, and an alternative cause is unlikely.

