### 5.4 Safety Endpoints

- Treatment emergent (S)AEs and SUSARs

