## 11.2 Serious Adverse Reactions and Unexpected Adverse Reactions

### 11.2.1 Definitions

#### ***Adverse Reaction:***

All noxious and unintended responses to a medicinal product related to any dose should be considered adverse drug reactions.

The phrase “responses to a medicinal product” means that a causal relationship between a medicinal product and an AE is at least a reasonable possibility, i.e. the relationship cannot be ruled out.

For marketed medicinal products, an adverse reaction is a response to a drug which is noxious and unintended and which occurs at doses normally used in man for prophylaxis, diagnosis, or therapy of disease or for modification of physiological function.

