#### ***Unexpected Adverse Reaction:***

An unexpected adverse reaction is defined as an adverse reaction, the nature or severity of which is not consistent with the applicable product information (e.g. IB for an unauthorised IMP or similar product information sheet such as the SPC).

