#### ***Suspected Unexpected Serious Adverse Reaction (SUSAR):***

A SUSAR is defined as any serious adverse reaction that might be related to the IMP and is unexpected according to the definition above.

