6.16 Safety Evaluation

6.16.1 Adverse Events

Adverse events (AEs) will be coded using the latest MedDRA dictionary version. The version used will be indicated in the data summaries and listings.

A treatment-emergent adverse event (TEAE) is defined as an AE that started on or after the start of the administration study treatment. If adverse event dates are incomplete and it is not clear whether the adverse event was treatment-emergent, it will be assumed to be treatment-emergent.

Any AE commencing after the last administration of study treatment may be considered treatment emergent.

A summary table by treatment and overall will present the following:

- TEAEs (events and patients).
- Serious TEAEs (events and patients).
- Serious study treatment related TEAEs (events and patients).
- TEAEs by pattern (intermittent/continuous/single event) (events and patients).
- TEAEs by severity (mild/moderate/severe) (events and patients).
- TEAEs by relationship to study treatment (events and patients).
- TEAEs leading to withdrawal from study (patients only).
- TEAEs leading to discontinuation of study treatment (patients only).
- Study treatment related TEAEs leading to discontinuation of study treatment (patients only).
- TEAEs leading to death (patients only).

In the above summaries, if a patient experienced more than one TEAE, the patient will be counted once using the most related event for the “by relationship to study treatment” and “related to study treatment” summaries and at the worst severity for the “by severity” summary. If a patient experienced more than one TEAE, the patient will be counted once for each pattern recorded. For summaries at the patient level, the number and percent of patients will be presented.

The above summary table will be presented for the pilot and double-blind phases.

The following tables will be presented:

- TEAEs by System Organ Class (SOC) and Preferred Term (PT).
- TEAEs by PT.
- TEAEs by SOC, PT and severity.
- TEAEs by SOC, PT and relationship to study treatment (related/ not related).
- Serious TEAEs by SOC and PT
- TEAEs leading to withdrawal by SOC and PT

For all of the above, SOC and PT will be presented in decreasing frequency of the total number of patients with TEAEs. Number of events and number and percentage of patients will be presented.

Further details of the above four tables are given below:

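### Protocol 11.1.3 and 11.2.1 set incompatible causality thresholds, so possible reactions may be recorded as not related or fit no category

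*Protocol*

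**What the plan says.** **Investigator's scale (Protocol 11.1.3).** There are two categories. *Related* requires that the timing is reasonable and that the event "follows a known response pattern to the treatment, and an alternative cause is unlikely". All three conditions are joined. An event is *Not related* if its timing "is not reasonable or another cause can explain the occurrence of the AE"; either limb is enough.

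**Reaction and SUSAR definitions (Protocol 11.2.1).** For an adverse reaction the standard is that "a causal relationship between a medicinal product and an AE is at least a reasonable possibility, i.e. the relationship cannot be ruled out". A reaction is unexpected if it is one "the nature or severity of which is not consistent with the applicable product information". A SUSAR is "any serious adverse reaction that might be related to the IMP and is unexpected according to the definition above".

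**Where causality is used.**
- Protocol 11.1.4 requires a relationship to be recorded for every AE. It also requires a preliminary causality assessment when a potential SAE is notified to the pharmacovigilance CRO.
- Protocol 11.2.2 has that CRO report SUSARs, but does not say whose causality judgement counts.
- SAP 6.16.1 tabulates events as related or not related, counts serious related events, and counts related events leading to discontinuation of study treatment.
- Protocol 7.5.2, 7.8 and 13.10 refer to events possibly or probably due to the study drug. Those are grades that 11.1.3 does not contain.

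**Safety endpoint (Protocol 5.4).** "Treatment emergent (S)AEs and SUSARs".

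**The concern.** Section 11.1.3 is the only causality scale the investigator is given, and it asks for more evidence than the protocol's own definition of an adverse reaction. Two features of this trial make the gap matter. Protocol 1.6 reports no related SAEs with DS102 so far, so the documents show no serious response pattern to match. Protocol 1.1 describes a disease that often leads to failure of several organs, with mortality above 30%, so another explanation is at hand for many serious events.

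At stake are the related-event tables in the SAP, the causality information that reaches the pharmacovigilance CRO, and the clarity of the attribution step in the discontinuation and stopping provisions.

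**Working it through.** The documents state no expected number of related events or SUSARs, so there is no figure to reproduce. The check applies both sets of definitions, as written, to each type of event.

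| Event | Category in 11.1.3 | Status in 11.2.1 | Agree? |
|---|---|---|---|
| A. Reasonable timing, known pattern, alternative cause unlikely | *Related* | Adverse reaction; SUSAR if serious and unexpected, for example in severity | Yes |
| B. Reasonable timing, no other cause, pattern not known | Neither: fails *Related* on pattern and fails both limbs of *Not related* | Adverse reaction if causality is a reasonable possibility; SUSAR if also serious and unexpected | No |
| C. Reasonable timing, another cause can explain it, drug cannot be ruled out | *Not related* | Adverse reaction; SUSAR if serious and unexpected | No |
| D. Timing not reasonable | *Not related* | Ordinarily not a reaction | Yes |

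**Row B.** Section 11.1.4 requires a relationship for every AE, yet the scale has no place for this one. The investigator must either relax the wording of *Related* or stretch that of *Not related*. The protocol does not say which, so sites may differ.

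**Row C.** As an illustration, take a serious bleed during treatment in a patient with coagulopathy. The liver disease can explain it, which is enough for *Not related* in 11.1.3. If the drug cannot be excluded, the same event is an adverse reaction in 11.2.1.

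**Effect on the SAP tables.** SAP 6.16.1 uses a binary related / not related split. Row C events fall on the not-related side. Row B events fall wherever the site puts them. Both can only reduce the related count compared with the 11.2.1 standard, and the count of serious related events is exposed in the same way.

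**Effect on SUSARs.** The SUSAR definition rests on an event that might be related, not on the 11.1.3 category. On its own wording it admits rows A, B and C. It would narrow only if the 11.1.3 category were used as the entry condition, and no section says that it is or is not.

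**Effect on discontinuation and stopping.** Sections 7.5.2, 7.8 and 13.10 need a possible or probable grade of attribution. A two-level scale cannot supply one, so the protocol does not show how the recorded causality feeds these provisions.

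**The case against.** A reader might infer that the SUSAR part of the safety endpoint is nearly empty by construction, because a reaction of a new kind cannot follow a known pattern. The documents do not support that. SUSARs are defined through 11.2.1, and unexpectedness covers severity as well as nature. Section 11.1.3 also does not equate a known response pattern with what is listed in the product information, so treating the two as the same is an interpretation. SAP 6.25 places SUSAR reporting outside the SAP, so no planned SUSAR analysis is emptied.

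Nor is it shown that expedited reporting would fail. Under 11.1.4 every potential SAE goes to the pharmacovigilance CRO within 24 hours whatever its causality, and the assessment sent with it is only preliminary. The unassigned decision is an ambiguity, not a demonstrated failure. It would also be wrong to say that new toxicity is always filed as *Not related*: the clearest case, row B, has no category at all.

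Several safeguards do not depend on attribution:
- All treatment-emergent AEs and SAEs belong to the safety endpoint.
- SAP 6.16.1 tabulates all such events, serious events, and events leading to death or discontinuation by arm.
- Potential severe liver injury is handled whatever its presumed cause, with adjudication by an independent expert within 24 hours (Protocol 11.3.1).
- The DSMB reviews accumulating data (Protocol 13.3).
- Attribution is made blind, by the same rule in both arms.

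All of this stands, and it limits the consequence. It does not remove the conflict between the two thresholds or close the gap in row B. Blinding prevents the arms from being treated differently, but it does not restore events to the related count.

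**Conclusion.** The point holds as an internal inconsistency. Sections 11.1.3 and 11.2.1 apply different causality thresholds, the two categories in 11.1.3 do not cover every event, and the attribution grades in 7.5.2, 7.8 and 13.10 do not exist on that scale. The related and serious related event tables may understate related events. The overall tables of treatment-emergent and serious events are not affected.

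The conclusion rests on a literal reading, with the conditions for *Related* all required. An investigator who relied on judgement instead would misclassify fewer events. An effect on SUSAR identification needs the further assumption that the 11.1.3 category acts as the gate. The documents do not allow a count of the events affected.

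**What to change.** 1. In 11.1.3, define *Related* by the 11.2.1 standard, a causal relationship that is at least a reasonable possibility, and *Not related* as no reasonable possibility. Every event then has exactly one category.
2. Keep timing, known pattern and alternative causes as factors to weigh, not as deciding conditions.
3. Judge expectedness separately from causality.
4. State in 11.2.2 whose causality assessment decides SUSAR status.
5. Reconcile the attribution wording in 7.5.2, 7.8 and 13.10 with the two-level scale, so that it is clear how a recorded causality maps to those provisions. Which clinical rule should apply is for the sponsor and its medical advisers.

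The cost is protocol wording and matching eCRF and SAE-form text. The SAP tables keep their layout. The downside is that somewhat more events will be recorded as related and assessed for expedited reporting.

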### 11.1.4 Reporting of AEs and SAEs

All AEs must be recorded in the eCRF, defining relationship to IMP and severity.

**As soon as the Investigator is aware of a potential SAE, he/she should contact the pharmacovigilance (PV) contract research organisation (CRO) monitor by phone, fax or e-mail, and, in any case, no later than 24 hours after the knowledge of such a case. The contact information is provided in the ISF.**

At the time of the call, the Investigator must provide, as a minimum requirement, the patient number, birth date, nature of the SAE and a preliminary assessment of causality. The Investigator should follow-up the initial notification of the potential SAE by faxing a copy of the SAE reporting form to the PV CRO at the number provided in the ISF. The faxed SAE reporting form should be sent to the PV CRO within 24 hours of knowledge of such a case.

Follow-up information on an existing SAE that is fatal or life-threatening should be reported by the Investigator to the PV CRO within five days after the initial report. Where appropriate, hospitalisation or autopsy reports should be made available. All SAEs will be followed up until resolution (i.e., asymptomatic, stabilization or death).

AEs should be reported from the first dose of study drug up to and including the follow up period. Following completion of the study, if the Investigator becomes aware of any AE that is potentially related to the IMP the Sponsor should be notified.

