## 6 STUDY DESIGN

### 6.1 General

This is a randomised, placebo-controlled, double-blind, parallel group, multicentre, exploratory phase II study preceded by an open label pilot phase to investigate the efficacy and safety of orally administered DS102 capsules in patients with acute decompensated AH aged over 18 years.

After the completion of the open-label phase of the study the DSMB will evaluate the safety and pharmacokinetic data and might recommend a dose adjustment for the double blind randomised phase of the study

After the open-label pilot phase of the study during which six patients will be enrolled, two parallel groups of patients will be enrolled into the randomised double-blind phase of the study to compare one dose of DS102 with placebo over a 28 day treatment period. Patients will receive standard of care therapy in addition to their assigned IMP throughout the treatment period of the study. It is planned that 120 evaluable patients, 60 per treatment group, will be randomised.

Both parts of the study, the open label phase and the double blind phase of the study consist of a screening period of up to five days (at the discretion of the investigator), a 28 day treatment period and a follow up period until day 90 after start of treatment. Screening is to commence upon admission to hospital; at the screening visit, after giving informed consent to participate, patients will be assessed using the screening examinations.

A schematic diagram of the overall timeframe of the study is given in Figure 3.

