## 8 STUDY CONDUCT

### 8.1 Study Schedule

During the study, 8 visits to the clinic are scheduled after the screening visit (Visit 1): one at the start of the comparative treatment period (Baseline/Visit 2) and six in the comparative treatment period (Visit 3/Day 3, Visit 4/Day 5, Visit 5/Day 7, Visit 6/Day 14, Visit 7/Day 21, Visit 8/Day 28 or Early Termination).

A final safety follow-up visit (Visit 9/Day 90) will be conducted on Day 90.

For patients who discontinue the study early, for whatever reason, the Early Termination visit (Visit 8) will be performed. Patients who discontinue the study before Day 28 and are already discharged from the hospital will be asked to attend the investigative site as soon as possible that assessments scheduled for Visit 8 can be conducted. These patients will be asked also to attend a final safety follow-up visit (Visit 9/Day 90).

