### **8.2.9 Visit 8/Day 28/Early Termination**

The following assessments will be performed:

- Physical examination (as detailed in Section 9.2.2)
- Vital signs (blood pressure, heart rate and body temperature), as detailed in Section 9.2.4);
- ECG (as detailed in Section 9.2.3)
- Pharmacokinetic sampling (as detailed in Section 9.2.8.1)
- Exploratory blood sampling (as detailed in Section 9.2.8.2)
- Samples for clinical laboratory safety tests (haematology, serum biochemistry, and coagulation tests as detailed in Section 9.2.5)
- Pregnancy test (as detailed in Section 9.2.7)
- MELD (as detailed in Section 9.1.1)
- MDF (as detailed in Section 9.1.7)
- m-SOFA (as detailed in Section 9.1.8)
- APACHE II score (as detailed in Section 9.1.9)
- Total bilirubin (as detailed in Section 9.1.2)
- CK-18 (as detailed in Section 9.1.6)
- AST:ALT (as detailed in Section 9.1.3)
- Child pugh score (as detailed in Section 9.1.5)

- Gamma GT (as detailed in Section 9.1.4)
- Biomarker (as detailed in Section 9.2.8.3)
- West Haven criteria assessment (as detailed in Section 9.1.11)
- Lille score assessment (as detailed in Section 9.1.10)
- Collection of acute kidney injury, ascites and variceal haemorrhage data
- AE assessment (as detailed in Section 11)
- Concomitant medication assessment (as detailed in Section 9.2.10)

In addition, the following assessments of nutritional status will also be performed, with nutritional interventions provided where required:

- BMI
- Bedside Subjective Global Assessment (SGA) score (0, 1, 2, and 3). Patients will be classified into the following categories:
  - Well nourished (0)
  - Mild malnutrition (1)
  - Moderate malnutrition (2)
  - Severe malnutrition (3)

The IMP or placebo will be returned. Further IMP or placebo will not be supplied to the patient.

On completion of this visit, patients will be advised that they will be required to return to the investigational site in 62 days at Visit 9 for final assessment.

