### **8.2.10 Visit 9/Day 90/Follow Up**

In case of the patient's survival the following assessments will be performed:

- Physical examination (as detailed in Section 9.2.2)
- Vital signs (blood pressure, heart rate and body temperature), as detailed in Section 9.2.4);
- Samples for clinical laboratory safety tests (haematology, serum biochemistry, and coagulation tests as detailed in Section 9.2.5)
- MELD ( as detailed in Section 9.1.1)
- MDF (as detailed in Section 9.1.7)
- m-SOFA (as detailed in Section 9.1.8)
- West Haven criteria assessment (as detailed in Section 9.1.11)
- Lille score assessment (as detailed in Section 9.1.10)
- APACHE II score (as detailed in Section 9.1.9)
- Total bilirubin (as detailed in Section 9.1.2)
- CK-18 (as detailed in Section 9.1.6)

---

- AST:ALT (as detailed in Section 9.1.3)
- Child pugh score (as detailed in Section 9.1.5)
- Gamma GT (as detailed in Section 9.1.4)

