## 15. 2 Appendix 2: Study Flowchart – Double-Blind Phase

Visit	Screening/ Visit 1	Baseline/ Visit 2	Day 3/ Visit 3	Day 5/ Visit 4	Day 7/ Visit 5	Day 14/ Visit 6	Day 21/ Visit 7	Day 28/Visit 8/ Early Termination	Day 90/Visit 9/ Follow Up
Day		0	3	5	7	14	21	28	90
Visit Window	N/A	±0 day	±0 day	±0 day	±2 day	±2 day	±2 day	±1 day	±10 days
Informed Consent 	X								
Inclusion/Exclusion	X	X							
Demographics	X								
Patient Randomisation		X							
Medical History	X	X							
Physical Examination	X	X	X	X	X	X	X	X	X
Vital Signs	X	X	X	X	X	X	X	X	X
ECG (6-lead or 12-lead)	X	X							X
Pharmacokinetic Sampling 		X	X	X	X	X	X	X	
Exploratory Blood Sample		X				X		X	
Clinical Laboratory Tests 	X	X	X	X	X	X	X	X	X
Virology	X								
Urinalysis	x								
Liver ultrasound	X								
Pregnancy Test 	X	X				X		X	
MELD	X	X	X	X	X	X	X	X	X
MDF	X	X	X	X	X	X	X	X	X
m-SOFA		X	X	X	X	X	X	X	X
West Haven Criteria	X	X	X	X	X	X	X	X	X
APACHE II		X	X	X	X	X	X	X	X
Lille score		X	X	X	X	X	X	X	X
Total Bilirubin	X	X	X	X	X	X	X	X	X
CK-18		X	X	X	X	X	X	X	X
ALT, AST	X	X	X	X	X	X	X	X	X
Child Pugh Score		X	X	X	X	X	X	X	X
Gamma GT		X	X	X	X	X	X	X	X
Assessment of nutritional status		X				X		X	
Collection of acute kidney injury, ascites and variceal haemorrhage data		X	X	X	X	X	X	X	
Biomarker		x	x	x	x	x	x	x	

Visit	Screening/ Visit 1	Baseline/ Visit 2	Day 3/ Visit 3	Day 5/ Visit 4	Day 7/ Visit 5	Day 14/ Visit 6	Day 21/ Visit 7	Day 28/Visit 8/ Early Termination	Day 90/Visit 9/ Follow Up
Mortality			X	X	X	X	X	X	X
IMP/Placebo Administration		X -----X							
AE Assessment		X	X	X	X	X	X	X	
Concomitant Medication Assessment	X	X	X	X	X	X	X	X	

 Includes biochemistry, haematology, and coagulation tests. Caeruloplasmin will be collected at screening only

 Female Patients of child bearing potential only.

 Patient may be required to reconsent after Visit 1 if new information is made available.

 Trough plasma PK samples will also be obtained prior to the first daily dose on the indicated days.

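### AE reporting and concomitant-medication recording are required to the end of the study, but neither is scheduled after Day 28, so some late non-fatal events depend on spontaneous report

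*Protocol*

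**What the plan says.** The reporting duty is explicit. Protocol Section 11.1.4: "AEs should be reported from the first dose of study drug up to and including the follow up period". Section 6.1 fixes the end of that period, describing "a 28 day treatment period and a follow up period until day 90 after start of treatment". Section 8.1 gives the last visit a safety purpose: "A final safety follow-up visit (Visit 9/Day 90) will be conducted on Day 90". At Visit 8 patients are told that they are "required to return to the investigational site in 62 days at Visit 9 for final assessment". Section 9.2.10 asks for all concomitant medications to be recorded for as long as the study lasts.

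The schedule says something else. Section 8.2.10 opens with "In case of the patient's survival the following assessments will be performed" and lists 14 items: physical examination, vital signs, laboratory tests and eleven scores or markers. AE assessment and concomitant-medication assessment are not among them. In Appendices 1 and 2 the "AE Assessment" row and the concomitant-medication row are both blank at Day 90.

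Treatment-emergent (S)AEs and SUSARs are the only safety endpoint in Section 5.4. SAP Section 6.16.1 defines a TEAE as an AE starting on or after the first administration and sets no end date. It then adds, permissively, that an AE starting after the last dose may count.

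**The concern.** The governing text and the visit schedule disagree about whether AEs and medications are actively asked about after treatment stops. A site that follows the visit list and flow chart literally would meet its Visit 9 schedule without asking what happened since Day 28.

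The events at risk are non-fatal ones that are over, or leave no visible trace, by Day 90. Readmission is a natural example: Section 1.1 associates the disease with repeated hospitalisation, and Section 11.1.1 makes hospitalisation a criterion for seriousness. A readmission to another hospital at, say, Day 50 is a potential SAE that the investigator may never hear of. The dedicated collection of acute kidney injury, ascites and variceal haemorrhage also ends at Day 28, in line with its 28-day endpoints, so after that date AE reporting is the main route for such events if they are not fatal. Medication records matter too, because Section 11.1.3 tells the investigator to consider concomitant medications when judging causality.

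**Working it through.** **Step 1. Required period.** First dose (Day 0) to the end of follow-up (Day 90), from Sections 11.1.4 and 6.1.

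**Step 2. Scheduled assessments.** Each flow chart has nine visit columns. The rows below read the same in Appendices 1 and 2.

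| Row | Marked at | Marks | In the Visit 9 list? |
|---|---|---|---|
| AE assessment | Days 0, 3, 5, 7, 14, 21, 28 | 7 | No |
| Concomitant medication | Screening and Days 0 to 28 | 8 | No |
| Mortality | Days 3, 5, 7, 14, 21, 28, 90 | 7 | No |
| MELD | Screening to Day 90 | 9 | Yes |

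The seven AE marks match the seven visit lists that name an AE assessment (Visits 2 to 8, Sections 8.2.3 to 8.2.9). Other rows do carry a Day 90 mark. The blank is therefore unlikely to be a table-reading error. The missing mark at screening is expected, since AEs are defined from the first dose.

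**Step 3. Length of the interval.**
- Nominal: 90 − 28 = 62 days, which reproduces the protocol's own figure in Section 8.2.9.
- With the visit windows (Day 28 ±1, Day 90 ±10): shortest (90 − 10) − (28 + 1) = 51 days; longest (90 + 10) − (28 − 1) = 73 days.
- Share of the 90-day study: 62/90 = 0.69. This is calendar time only.
- For patients who leave the study early, the Visit 8 assessments are done sooner, so the interval can be longer. Termination at Day 14, for illustration, gives 90 − 14 = 76 days.

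**Step 4. What is still captured between Day 28 and Day 90.**
- Deaths: Section 7.5 and the mortality row of both charts.
- SAEs that the investigator learns of: 24-hour reporting under Section 11.1.4.
- Changes on examination and clinically significant vital-sign findings at Visit 9: to be recorded as AEs (Sections 9.2.2 and 9.2.4).
- Laboratory results at Visit 9: reviewed by the investigator for clinical significance (Section 9.2.8).

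What remains is the non-fatal event, unknown to the investigator, that has resolved or shows nothing on the day.

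**Step 5. Effect of the change.** Scheduled AE assessments rise from 7 to 7 + 1 = 8, the last at Day 90. The whole period is then covered by a scheduled enquiry, but the last 62 days by one retrospective question only.

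**The case against.** The best defence is that the duty itself is not missing. Section 11.1.4 is an express instruction covering follow-up, and the schedule merely fails to repeat it. Nor is the Visit 9 list exhaustive: mortality is due at Day 90 in both charts and is absent from the list. That is fair. Absence from Section 8.2.10 is weak evidence alone, and the two flow charts carry the point. How sites would act also depends on the eCRF and monitoring materials, which are not in the documents.

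A reader might infer several stronger things that the documents do not support:

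- **That late AEs are captured only if the patient volunteers them.** Step 4 shows other routes. Section 9.2.2 also directs the examination by the patient's symptoms, which invites some enquiry.
- **That 69% of the safety information is lost.** That figure is time, not events. The interval is off drug, and Section 1.6 gives a half-life of about two hours in healthy volunteers. The documents allow no estimate of the number of missed events. The half-life does not remove the conflict, however, because the protocol itself chose to extend reporting through follow-up.
- **That the comparison between arms is biased.** Randomisation is in permuted blocks stratified by site (Section 12.2) and site staff are blinded (Section 12.4). Differences between sites in how hard they ask should fall about equally on both arms. The likely result is under-counting in both.
- **That the SAP counts every AE to Day 90 as treatment-emergent.** Its definition has no end, but its sentence on events after the last dose is permissive. This is an ambiguity in the SAP that a change to the visit schedule alone would not settle.

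**Conclusion.** The inconsistency stands. Section 11.1.4 requires AE reporting to Day 90 and Section 9.2.10 requires medication recording for the whole study, while Section 8.2.10 and both flow charts schedule neither after Day 28. The interval is 62 days nominally, 51 to 73 days within the visit windows, and longer after early termination.

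The consequence is limited: possible under-counting of non-fatal late events that leave no finding at Visit 9, probably in both arms, in tables whose TEAE window has no stated end. This assumes that at least some sites treat the flow chart and visit list as complete, which the documents cannot confirm. The primary and other efficacy analyses are not touched. The point still deserves correction, because it concerns the trial's only safety endpoint and the remedy is small.

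**What to change.** 1. Add AE assessment and concomitant-medication assessment to the Visit 9 list in Protocol Section 8.2.10 (two list items).
2. Add both to the Day 90 column of Appendices 1 and 2: 2 rows × 2 charts = 4 cells.
3. In SAP Section 6.16.1, state when the TEAE window closes so that it matches Section 11.1.4, and replace the permissive sentence on events after the last dose with a definite rule.

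The cost is a protocol amendment, with submission for approval if it is judged substantial under Section 13.1, a short SAP revision, and a few minutes of site time. Visit 9 already takes place, so no visit or sample is added. The limit is recall: one question at Day 90 covers about two months, so some minor or resolved events will still be missed.
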